10.2.2. Subject withdrawal from investigational vaccine

A ‘withdrawal’ from the investigational vaccine refers to any subject who does not receive the complete treatment, *i.e.* when no further planned dose is administered from the date of withdrawal. A subject withdrawn from the investigational vaccine may not necessarily be withdrawn from the study as further study procedures or follow-up may be performed (safety or immunogenicity) if planned in the study protocol (see also Section 7.5).

Information relative to premature discontinuation of the investigational vaccine will be documented on the Vaccine Administration screen of the eCRF. The investigator will document whether the decision to discontinue further vaccination was made by the subject himself/ herself or by the investigator, as well as which of the following possible reasons was responsible for withdrawal:

- SAE.
- Non-serious AE.
- Other (specify).

10.3. Screening failures

Screening failures are defined as subjects who are withdrawn from the study after giving informed consent, but who do not meet the inclusion and exclusion criteria.

The following information will be collected for screening failures:

- Informed consent.
- Demographic data.
- Inclusion/exclusion criteria.
- SAEs related to study participation that occurred after signing informed consent.
- Screening conclusion.

11. STATISTICAL METHODS

11.1. Primary endpoints

- Occurrence of each solicited local adverse event (AE), during the 7-day follow-up period (*i.e.* day 0 - 6) following each vaccination, in all subjects.
- Occurrence of each solicited general AE, during the 7-day follow-up period (*i.e.* day 0 - 6) following each vaccination, in all subjects.
- Occurrence of any unsolicited AE, during the 30-day follow-up period (*i.e.* day 0 - 29) following each vaccination, in all subjects.

- Occurrence of each haematological/ biochemical laboratory abnormality at Day 0, Day 7, Day 30, Day 60, Day 67, Day 90, Day 270 and Day 450, in all subjects.
- Occurrence of any potential immune-mediated disease (pIMD) from first vaccination up to study conclusion, in all subjects.
- Occurrence of any serious adverse event (SAE) from first vaccination up to study conclusion, in all subjects.

11.2. Secondary endpoints

- Anti-PD, anti-PE and anti-PilA total IgG antibody concentrations as measured by ELISA, at Day 0, Day 30, Day 60, Day 90, Day 270 and at Day 450, in all subjects.
- NTHi-specific cell-mediated immune responses as measured by flow cytometry intracellular cytokine staining (ICS) (frequency of specific CD4⁺/CD8⁺ T-cells expressing two or more markers, such as IL-2, IL-13, IL-17, IFN- γ , TNF- α and CD40L), at Day 0, Day 90, Day 270 and at Day 450, in a sub-cohort of subjects.

11.3. Tertiary endpoints (Amended 15 April 2016)

- Number of cases of NTHi-associated moderate and severe AECOPD, over a period starting 1 month post-Dose 2 and lasting for 1 year, in all subjects.
- Number of cases of NTHi-associated AECOPD (any severity), over a period starting 1 month post-Dose 2 and lasting for 1 year, in all subjects.
- Number of cases of moderate and severe AECOPD (any cause), over a period starting 1 month post-Dose 2 and lasting for 1 year, in all subjects.
- Number of cases of AECOPD (any cause, any severity), over a period starting 1 month post-Dose 2 and lasting for 1 year, in all subjects.
- Time to first AECOPD, in all subjects.
- Assessment of EXACT-PRO score, daily at bedtime throughout the study, in all subjects.
- NTHi presence in sputum, at Screening, Day 90, Day 180, Day 270, Day 360 and Day 450, and from first vaccination to study conclusion for each AECOPD, in all subjects.
- Assessment of *CAT* score, at Screening, Day 270 and Day 450, and from first vaccination to study conclusion for each AECOPD, in all subjects.
- Assessment of SGRQ-C score, at Screening, Day 270 and Day 450, in all subjects.
- Assessment of mMRC scale, at Screening, Day 270 and Day 450, and from first vaccination to study conclusion for each AECOPD, in all subjects.
- Occurrence of rescue medication use, over a period starting 1 month post-Dose 2 and lasting for 1 year, in all subjects.
- Occurrence of healthcare use for AECOPD, over a period starting 1 month post-Dose 2 and lasting for 1 year, in all subjects.

[figure not shown]
- Assessment of FEV1% of predicted normal value at Screening, Day 270 and Day 450, in all subjects.
- Assessment of 6MWT score, at Screening and Day 450, in all subjects.
- Occurrence of selected biomarkers in a subset of blood samples, at Day 0 and Day 450, and from first vaccination to study conclusion for each AECOPD, in all subjects.
- Presence of respiratory viral pathogens in sputum (including respiratory syncytial virus, parainfluenza virus, enterovirus/ rhinovirus, metapneumovirus, influenza virus, adenovirus, bocavirus and coronavirus) at Screening, Day 90, Day 180, Day 270, Visit Day 360 and Day 450 and at each AECOPD visit from first vaccination to study conclusion, in all subjects.*

11.4. Determination of sample size

This study is a Phase II safety study to assess safety and reactogenicity of the investigational vaccine in moderate and severe COPD patients.

Considering the sample size of 70 in the group 10-AS01E, [Figure 4](#) illustrates the probability of detecting an AE with true occurrence rate 0 - 10%.

Figure 4 Probability not to observe an AE for 60, 70 or 80 subjects per group

From [Figure 4](#), it can be seen that with a sample size of 70 subjects per group, there is more than 50% of chance to detect an AE with a true incidence of 1%, and more than 97% of chance to detect an AE with a true incidence of 5%.

11.5. Study cohorts to be analysed

The following study cohorts will be evaluated.

11.5.1. Total vaccinated cohort

The Total vaccinated cohort (TVC) will include all subjects with at least 1 study vaccine administration documented:

- A **safety** analysis based on the TVC will include all vaccinated subjects.
- An **immunogenicity/ efficacy** analysis based on the TVC will include all vaccinated subjects for whom immunogenicity/ efficacy data are available.

The TVC analysis will be performed per treatment actually administered at Dose 1.

11.5.2. ATP cohort for analysis of immunogenicity

The ATP cohort for immunogenicity will include all subjects in the TVC:

- Who met all eligibility criteria.
- For whom the administration route and site of the vaccines was according to protocol.
- Who complied with the vaccination schedule, as specified in [Table 9](#).
- Who received the study vaccines according to protocol procedures.
- Who did not receive a concomitant medication/ product leading to elimination from the ATP analysis for immunogenicity (see Section [7.6.2](#)), up to the 1 month post-Dose 2 visit (Day 90).
- Who did not present with an intercurrent medical condition leading to elimination from the ATP analysis for immunogenicity (see Section [7.7](#)), up to the 1 month post-Dose 2 visit (Day 90).
- Who complied with the blood sample timings as specified in [Table 9](#), at the 1 month post-Dose 2 visit (Day 90).
- For whom post-vaccination immunogenicity results are available for at least 1 assay.

11.5.3. ATP cohort for analysis of persistence of immunogenicity

The ATP cohort for persistence of immunogenicity will include all evaluable subjects, *i.e.*, those who were included in the ATP cohort for immunogenicity, or were excluded from this cohort solely because they had no blood samples taken or because of incompliance with blood sample timings up to the 1 month post-Dose 2 visit, and:

- Who did not receive a concomitant medication/ product leading to elimination from the ATP analysis for immunogenicity (see Section [7.6.2](#)).
- Who did not present with an intercurrent medical condition leading to elimination from the ATP analysis for immunogenicity (see Section [7.7](#)).

- Who complied with the blood sample timings after the 1 month post-last vaccination visit as specified in [Table 9](#).
- For whom persistence immunogenicity results are available for at least 1 assay.

11.5.4. ATP cohort for analysis of efficacy

The ATP cohort for analysis of efficacy will include all subjects in the TVC:

- Who met all eligibility criteria.
- For whom the administration route and site of the vaccines was according to protocol.
- Who complied with the vaccination schedule, as specified in [Table 9](#).
- Who received the study vaccine according to protocol procedures.
- Not having received a medication/ product/ vaccine that may lead to elimination from the ATP analysis for efficacy (see Section [7.6.3](#)).

11.6. Derived and transformed data

The study groups will be defined by treatment actually administered at Dose 1.

Demography

- For a given subject and a given demographic variable, missing measurement will not be replaced.

Safety

- For solicited symptoms, the analysis will exclude subjects with missing or un-evaluable measurements (*i.e.* total analysis of solicited symptoms will include all vaccinated subjects with documented solicited symptom sheets).
- For the unsolicited symptoms and concomitant medications/ products/ vaccinations, subjects who miss reporting symptoms/concomitant medications/ products/ vaccinations will be treated as subjects without unsolicited symptoms or concomitant medications/ products/ vaccinations, respectively.

Immunogenicity

- For a given subject and the analysis of a given immunogenicity measurement, missing or un-evaluable measurements will not be replaced.
- A seronegative subject is defined as a subject whose antibody concentration is below the assay cut-off value.
- A seropositive subject is defined as a subject whose antibody concentration is greater than or equal to the assay cut-off value.
- Antibody concentrations below the assay cut-off will be given an arbitrary value of half the assay cut-off for the purpose of geometric mean concentration (GMC) calculation.

- Calculation of the GMCs will be performed by taking the anti-logarithm in base 10 (anti-log10) of the mean of the log10 concentration transformations.

Impact of the investigational vaccine on AECOPD

- For a given subject and the analysis of a given laboratory assay, missing or un-evaluable measurements will not be replaced.
- Subjects who did not have any sputum collected during at least 1 AECOPD (if at least 1 AECOPD occurred) will not be taken into account for the NTHI-associated AECOPD analyses.
- For summaries of the number of AECOPD occurring during the 1 year follow-up period starting 1 month post-Dose 2, an exacerbation rate will be calculated for each subject. The number of exacerbations during the 1-year follow-up period will be imputed for subjects withdrawing from the study to provide an estimate of the number of exacerbations over the follow-up period. This calculation will only be performed for purposes of reporting summary statistics for the rate of exacerbations during the 1 year follow-up period since the modelling of exacerbations takes into account the number of exacerbations and the time of follow-up for each subject. The calculation of exacerbation rate will be based on follow-up period intervals to avoid obtaining high imputed rates if a subject withdrew very early in the follow-up period after experiencing an exacerbation. Since treatment courses for moderate/severe exacerbations are \leq 2 - 4 weeks when appropriate, calculated numbers of exacerbations for subjects withdrawing from the study will be based on 4-week intervals of the follow-up period. For subjects followed for less than 1 year, the number of exacerbations during the 1-year follow-up period will be calculated by multiplying the number of exacerbations experienced by the subject by 13 and dividing by the number of 4-week periods the subject was followed up [[Stockley, 2006](#)]:

Number of exacerbations per year = Number of exacerbations * 13 /Number of 4-week treatment period intervals

HRQOL

- The CAT index will be derived as the sum of the ratings recorded for each of the eight individual items. Each of these items has 6 possible scores (0, 1, 2, 3, 4 or 5), leading to a range of 0 to 40 for CAT score.

11.7. Analysis of demographics

Demographic characteristics (age at the first dose in years, gender and geographical ancestry) and cohort description will be summarized by group using descriptive statistics:

- Frequency tables will be generated for categorical variable such as geographical ancestry;
- Mean, median and standard error will be provided for continuous data such as age.

The distribution of subjects enrolled among the study sites will be tabulated as a whole and per group.

Withdrawal status will be summarised by group using descriptive statistics:

- The numbers of withdrawn subjects will be tabulated according to the reason for withdrawal.
- The number of subjects enrolled into the study as well as the number of subjects excluded from ATP analyses will be tabulated.

11.8. Analysis of safety

The analysis will be performed on the TVC. If the percentage of vaccinated subjects excluded from the ATP cohort for efficacy is at least 10%, a second analysis will be performed on the ATP cohort for efficacy to complement the first analysis.

The percentage of subjects with at least one **local AE** (solicited and unsolicited), with at least one **general AE** (solicited and unsolicited) and with any AE during the 7-day (day 0 – day 6) or the 30-day (day 0 – day 29) follow-up period will be tabulated after each vaccination and overall with exact 95% confidence interval (CI). The same computations will be done for Grade 3 AEs, for related AEs and for Grade 3 related AEs.

The percentage of subjects/doses reporting each individual solicited local (any grade, Grade 3) and general (any grade, Grade 3, related, Grade 3 related) AE during the 7-day (day 0 to day 6) follow-up period will be tabulated for each group as follows:

- Overall, the percentage of subjects with the symptom and its exact 95% CI.
- Overall, the percentage of doses with the symptom and its exact 95% CI.
- Per study vaccine dose, the percentage of subjects with the symptom and its exact 95% CI.

The exact 95% CIs will be calculated assuming independence between doses. For fever, additional analyses will be performed by 0.5°C increments.

The verbatim reports of **unsolicited** symptoms will be reviewed by a physician and the signs and symptoms will be coded according to the MedDRA Dictionary for Adverse Reaction Terminology. Every verbatim term will be matched with the appropriate preferred term (PT). The percentage of subjects with unsolicited symptoms during the 30-day follow-up period after any study vaccine dose with its exact 95% CI will be tabulated by group and by MedDRA PT. Similar tabulation will be done for the percentage of doses, for Grade 3 unsolicited symptoms, for unsolicited symptoms that resulted in a medically attended visit, for Grade 3 and causally related unsolicited symptoms and for unsolicited symptoms causally related to vaccination.

For each group and for each **haematology/ biochemistry parameter**:

- The percentage of subjects having results below or above the local laboratory normal ranges will be tabulated by time point.
- The maximum grading from Screening up to study conclusion will be tabulated. Grades will be based on the FDA Guidance for Industry “Toxicity Grading Scale for

Healthy Adults and Adolescent Volunteers Enrolled in Preventive Vaccine Clinical Trials" (see **APPENDIX C**).

The number of subjects who experienced any **pIMD** or any **SAE** from first vaccination up to 6 months post-Dose 2 will be reported.

The number of subjects who experienced any **AE leading to study withdrawal**, from first vaccination up to study conclusion, or any **SAE related to study participation of concurrent GSK medication/ vaccination**, during the entire study period, will be reported.

Pregnancy exposures from first vaccination up to 6 months after last vaccination and pregnancy outcomes will be described in detail.

The percentage of subjects/ dose using **concomitant medication/ product** (any medication/ product, any antipyretic and any antipyretic taken prophylactically, respectively) during the 7-day follow-up period (day 0 – day 6) and during the 30-day follow-up period (day 0 – day 29) will be summarised per group for each dose and overall per dose.

11.8.1. iSRC safety evaluations

Unblinded review of safety data will be done during iSRC evaluations (refer to Section **9.10** for more information). No individual clinical study report will be written as a result of these safety evaluations.

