7.5. Contraindications to subsequent vaccination

The following events constitute contraindications to administration of the investigational NTHi vaccine at that point in time; if any of these events occur at the time scheduled for vaccination, the subject may be vaccinated at a later date, within the time window specified in the protocol, or the subject may be withdrawn at the discretion of the investigator (see Section 9.5).

- Moderate or severe AECOPD that is on-going or that has not been resolved for at least 7 days at the time of vaccination.
- Acute disease and/ or fever at the time of vaccination.
 - Fever is defined as oral or axillary temperature $\geq 37.5^{\circ}\text{C}$. The preferred route for recording temperature in this study will be oral.
 - Subjects with a minor illness without fever can be administered all vaccines at the discretion of the investigator.

The following events constitute absolute contraindications to further administration of the investigational NTHi vaccine. If any of these events occur during the study, the subject must not receive vaccine Dose 2.

- Anaphylaxis following the administration of vaccine.
- Pregnancy.

- Any confirmed or suspected immunosuppressive or immunodeficient condition, based on medical history and physical examination (no laboratory testing required).
- Current immune-mediated disease other than COPD.
- Malignancy (excluding non-melanotic skin cancer and carcinoma *in situ* of the cervix, if considered cured) or lymphoproliferative disorder.
- Any other event which the investigator judges may put the safety of the subject at risk through vaccination.

For subjects meeting one of the above specified contraindications to subsequent vaccination before administration of vaccine Dose 2, the study visit at Day 67 (Visit 5) will be cancelled. These subjects will be invited to all other study visits as planned (including AECOPD-driven study visit[s] and/ or phone contact[s]) and will continue all study procedures as planned, with the exception of blood sampling for immunogenicity (humoral and CMI) and biomarkers and sputum sampling.

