7.6.1. Recording of concomitant medications/products and concomitant vaccination

All vaccinations and medications (except for vitamins and dietary supplements) administered throughout the study period (including dose, unit, frequency and reason for use) must be recorded in the eCRF.

7.6.2. Concomitant medications/products and vaccines that may lead to the elimination of a subject from ATP analysis for immunogenicity

The use of the following concomitant medications/products/vaccines will not require withdrawal of the subject from the study but may determine a subject's evaluability in the ATP analysis for *immunogenicity*.

- Any investigational or non-registered product (drug or vaccine) other than the study vaccine used at any time during the entire study period.
- A vaccine not foreseen by the study protocol administered during the period starting 30 days before and ending 30 days after each dose of vaccine*, with the exception of any influenza or pneumococcal vaccines which may be administered \geq 15 days preceding or following any dose of study vaccine.

* In case an emergency mass vaccination for an unforeseen public health threat (e.g. a pandemic) is organised by the public health authorities, outside the routine immunisation program, the time period described above can be reduced if necessary

for that vaccine provided it is licensed and used according to its summary of product characteristics (SmPC) or prescribing information (PI) and according to the local governmental recommendations and provided a written approval of the Sponsor is obtained.

- Immunoglobulins or any blood products administered at any time during the study period.
- Immunosuppressants or other immune-modifying drugs administered chronically (*i.e.* more than 14 days) at any time during the study period (*e.g.* methotrexate). Use of corticosteroids is allowed as per local treatment recommendations.

7.6.3. Concomitant medications/ products that may lead to the elimination of a subject from the ATP analysis for efficacy

In addition to the concomitant medications/ products/ vaccines described in the Section 7.6.2, the use of the following medications/ products will not require withdrawal of the subject from the study but may determine a subject's evaluability in the ATP analysis for *efficacy*.

- Underwent lung transplantation/ lung resection surgery at any time during the entire study period.
- Chronic use of antibiotics at any time during the entire study period.

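### The conditional second safety analysis uses the ATP cohort for efficacy, whose membership depends partly on post-vaccination events, so this supplementary table can understate dose-limiting reactions and some treated serious events

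*Protocol*

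**What the plan says.** For the main safety analysis, Protocol 11.8 states: "The analysis will be performed on the TVC". Protocol 11.5.1 adds that a safety "analysis based on the TVC will include all vaccinated subjects". SAP Amendment 1 says the same in 5.1 and 6.1.1.

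Both documents then add a conditional repeat. Once exclusions from the efficacy cohort reach 10% of those vaccinated, "a second analysis will be performed on the ATP cohort for efficacy to complement the first analysis". Neither document defines an ATP cohort for safety.

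Two of the criteria for the efficacy cohort in Protocol 11.5.4 look beyond the moment of vaccination:

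- **Schedule.** The criterion opens "Who complied with the vaccination schedule, as specified in" and points to Table 9, where Dose 2 falls 60 to 75 days after Dose 1.
- **Treatment.** "Not having received a medication/ product/ vaccine that may lead to elimination from the ATP analysis for efficacy". The list is in 7.6.3, which adds chronic antibiotics and lung transplantation or resection to the items in 7.6.2. One item in 7.6.2 reads "Immunoglobulins or any blood products administered at any time during the study period"; another is immunosuppressants or other immune-modifying drugs for more than 14 days. Both sections say that these may affect evaluability. Section 7.6.2 expressly permits corticosteroids.

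Protocol 7.5 lists absolute contraindications, including anaphylaxis, current immune-mediated disease, malignancy and any other event that the investigator considers a safety risk. It says: "If any of these events occur during the study, the subject must not receive vaccine Dose 2". Protocol 10.2.2 records SAE and non-serious AE among the reasons for stopping vaccination.

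**The concern.** A safety table should not select its subjects on the outcome it describes. The ATP cohort for efficacy was built to estimate vaccine efficacy in subjects who followed the protocol, and for that purpose a two-dose requirement is natural. For safety, it means that Dose 1 and overall reaction rates are computed among subjects who went on to receive Dose 2 on time. Receiving Dose 2 on time is a later event that the reaction itself can prevent.

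The same applies, more weakly, to the listed products. Some could be given because of a potential immune-mediated disease (pIMD) or an SAE, and both are primary endpoints (Protocol 11.1).

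The loss could differ by group, because one arm receives an AS01E-adjuvanted vaccine and the other saline. If reactions that stop Dose 2 occur mainly after the adjuvanted vaccine, the second table would make the groups look more alike than they are. What is at stake is the reading of that supplementary table beside the main one, in a trial whose primary objective is to describe safety.

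**Working it through.** **1. The plan's own safety figure.** Protocol 11.4 gives the chance of seeing at least one AE among 70 subjects as more than 50% at a true incidence of 1% and more than 97% at 5%. With P = 1 − (1 − p)^n:

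- p = 0.01, n = 70: 1 − 0.99^70 = 50.5%.
- p = 0.05, n = 70: 1 − 0.95^70 = 97.2%.

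Both statements reproduce. They refer to all 70 subjects in the group, which is the TVC.

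**2. The trigger.** 10% of 140 = 14 excluded subjects. Assume that they split 7 and 7, leaving 63 per group. Then 1 − 0.99^63 = 46.9% and 1 − 0.95^63 = 96.1%. This small loss comes from the smaller number alone, even if exclusion has nothing to do with AEs.

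**3. Who leaves the cohort.**

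| Event after Dose 1 | Rule | Status in the ATP efficacy cohort |
|---|---|---|
| Safety event that bars Dose 2 | 7.5, 11.5.4 | Out, on the plain reading of the schedule criterion |
| Vaccination stopped for an SAE or AE | 10.2.2, 11.5.4 | Out, on the same reading |
| Event that delays Dose 2 past day 75 | Table 9, 11.5.4 | Out, on the same reading |
| Event treated with a listed product | 7.6.2, 7.6.3 | May be out |
| Event treated with corticosteroids | 7.6.2 | Not excluded for that reason |
| Other AE, Dose 2 given on time | none | In |

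**4. Effect on a rate.** Let x of n vaccinees have the event and m be excluded, with k subjects in both sets. The TVC rate is x/n. The ATP rate is (x − k)/(n − m). Assume n = 70, x = 7 and m = 7. The intervals are exact (Clopper-Pearson) 95% limits.

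| Set | Events/subjects | Rate | 95% CI |
|---|---|---|---|
| TVC | 7/70 | 10.0% | 4.1–19.5 |
| ATP, k = 0 | 7/63 | 11.1% | 4.6–21.6 |
| ATP, k = 1 | 6/63 | 9.5% | 3.6–19.6 |
| ATP, k = 3 | 4/63 | 6.3% | 1.8–15.5 |
| ATP, k = 5 | 2/63 | 3.2% | 0.4–11.0 |
| ATP, k = 7 | 0/63 | 0% | 0–5.7 |

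If exclusion were unrelated to the event, the expected overlap would be 7 × 7/70 = 0.7 subjects, and the ATP rate would be (7 − 0.7)/63 = 10.0%, as in the TVC. The understatement therefore comes entirely from overlap beyond chance. Section 7.5 creates such overlap for events that bar Dose 2.

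**The case against.** The strongest reply is that no event is lost. The TVC analysis is the main one and keeps every vaccinated subject. The second run is conditional, descriptive and meant only to sit beside the first. A repeat without protocol deviators can also show whether ineligibility or faulty administration affected the results. All of this stands. A reader might infer that the trial's safety description is itself compromised; the documents do not support that.

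A reader might also infer that any treated adverse event is removed. It is not. Only the listed products and procedures count, elimination is discretionary, corticosteroids are allowed, and antipyretics and short antibiotic courses are not listed. Most solicited and unsolicited AEs neither stop Dose 2 nor require a listed product.

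Nor would a few dose-limiting reactions produce this table on their own. Three such subjects are 3/140 = 2.1%, and 11 more exclusions would be needed to reach 14. Grade 3 intensity is not in itself a contraindication under 7.5. An ATP rate of zero is the extreme of the range above, not its expected value.

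Exclusion of one-dose subjects is a reading, not a stated rule. Subjects barred from Dose 2 are following the protocol, and the elimination-code form cited in SAP 5.4 is not among the documents. The footnote to Table 9 attaches the Dose 2 window only to the immunogenicity cohort. However, 11.5.4 refers to the same table for the efficacy cohort, so the reading is the natural one.

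There are also safeguards: exclusion counts (11.7), reporting of AEs leading to study withdrawal (11.8), individual listings (11.14.1), unblinded safety review by the internal committee (9.10.2), and the advice to interpret comparisons with caution (11.13). They help a careful reader, but none corrects the rates in the second table.

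**Conclusion.** The point holds for the supplementary table only. If it is run, its rates are conditioned on events after vaccination. It can understate reactions that stop or delay Dose 2, and some pIMDs or SAEs treated with listed products, possibly more in the vaccine group. The TVC results are sound, and most AEs are little affected.

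The size cannot be fixed from the documents, because it depends on how many excluded subjects had the event. With 7 of 70 affected and 7 of 70 excluded, both assumed, the ATP rate runs from 11.1% with no overlap to 0% with complete overlap, against 10.0% in the TVC. The conclusion rests on the plain reading of the schedule criterion and on some exclusions being related to adverse events. The change is worth making because the bias is avoidable, although it does not threaten the primary description of safety.

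**What to change.** In Protocol 11.8 and SAP 6.1.1, replace the ATP cohort for efficacy in the second safety analysis with a supportive set defined only by facts fixed at each administration: eligibility, correct product, route and site. Keep one-dose subjects. Make no exclusion for a missed or late Dose 2, or for treatment received later. Dropping the second run is an equally good solution.

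If the run is kept as written, label the table as not for safety inference, state that its cohort depends on post-vaccination events, and list the excluded subjects' AEs by group and reason for exclusion.

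The cost is one cohort definition, or one set of tables fewer. No new data are needed, and the TVC analysis does not change.
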